#### 5.4.4.1 CPK Monitoring

If a CPK elevation is observed after administration of the study drug begins, CPK will be monitored as follows.

- If CPK is  $> 3 \times \text{ULN}$  after the start of study drug administration and the subject is asymptomatic, retest CPK to confirm the CPK value, preferably within approximately 1 week from the previous blood sampling. In addition, retest CPK weekly, starting from the date of the initial CPK elevation to  $> 3 \times \text{ULN}$ , until CPK is  $\leq 3 \times \text{ULN}$  or until the investigator or sub-investigator considers CPK to have achieved a steady state. If the retest cannot be performed within 1 week from the collection time of the blood sample with the CPK value because of which the monitoring was initiated, suspension or interruption of the study drug should be considered until results of the retest are known.
- If CPK is  $> 3 \times \text{ULN}$  already at baseline and is elevated to  $> 2 \times \text{baseline}$  after the start of study drug administration and the subject is asymptomatic, retest CPK to confirm the value, preferably within approximately 1 week from the previous blood sampling. In addition, retest CPK weekly, starting from the date of the initial CPK elevation to  $> 2 \times \text{baseline}$  value, until CPK is  $\leq 2 \times \text{baseline}$  or until the investigator or sub-investigator considers CPK to have achieved a steady state. If the retest cannot be performed within 1 week from the collection time of the blood sample with the CPK value because of which the monitoring was initiated, suspension or interruption of the study drug should be considered until the results of the retest are known.
- If CPK  $> 10 \times \text{ULN}$  is confirmed after the start of study drug administration, suspend or interrupt the administration of the study drug immediately and retest CPK (see Section 3.4.1, Suspension, Interruption, and Resumption of the Study Drug).
- If a symptomatic CPK elevation (CPK elevation  $> 1.5 \times \text{ULN}$ , accompanied by unusual severe myalgia, muscular weakness, and muscle twitching) is reported by the investigator or sub-investigator, the study will be discontinued (see Section 3.4, Discontinuation Criteria for Individual Subjects).

At the time of CPK monitoring, the following parameters will also be measured. The answers given in the subject questionnaire will be recorded in the eCRF.

- Laboratory tests  
(Parameters to be measured: CK-MB, troponin-T, aldolase)
- A targeted physical examination\* and subject questionnaire to assess muscle strength and tenderness  
\*: As part of the targeted physical examination, urinalysis (blood and microscopy) will be performed.

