### 3.4 Discontinuation Criteria for Individual Subjects

A discontinuation means that a subject who has enrolled in the study prematurely terminates study treatment prior to the completion of all protocol-required elements.

The subject is free to withdraw from the study treatment and/or study for any reason and at any time without giving reason for doing so and without penalty or prejudice. The investigator is also free to terminate a subject's involvement in the study at any time if this is considered necessary because of the subject's clinical condition.

Discontinuation Criteria for Individual Subjects:

The investigator/sub-investigator should discontinue the study if any of the following criteria are met:

1. Subject withdraws consent.
2. The study drug is not sufficiently effective, and a change in treatment method is deemed to be in the subject's best interest by the investigator or sub-investigator.
3. Symptomatic CPK elevation, defined as  $CPK > 1.5 \times ULN$  with severe unusual myalgia, muscular weakness, or muscle twitching\*.  
\* Muscle twitching: A condition in which there is a cramp in a muscle, such as cramps in the calves
4. Any event of myopathy defined as severe unusual myalgia, muscular weakness, and muscle twitching\* regardless of CPK level that persists for at least 2 weeks or that worsens rapidly within 2 weeks.  
\* Muscle twitching: A condition in which there is a cramp in a muscle, such as cramps in the calves
5. Subject infected with HBV who has tested positive for either of or both of HBc and HBs antibodies and is found to be positive for HBV-DNA assay during the study period. Abrupt discontinuance of immunosuppressive therapy may precipitate severe or fulminant hepatitis. Therefore, when HBV reactivates, nucleic acid analog therapy should be immediately initiated, and a hepatologist should be consulted regarding the continuation of ASP015K and concomitant DMARD (unique to Japan: as indicated by "Proposal for Management of Rheumatic Disease Patients with Hepatitis B Virus Infection Receiving Immunosuppressive Therapy" by the Japan College of Rheumatology).

- CONFIDENTIAL -

6. Subject has a malignant tumor.
7. Subject has an adverse event (AE) such as a serious infection, and the investigator or sub-investigator considers that it is not in the subject's best interest to continue the study.

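### The symptomatic-CPK discontinuation rule joins three muscle symptoms with 'or' in Section 3.4 and the Synopsis but with 'and' in Section 5.4.4.1, and no text says which governs

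*Protocol*

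**What the plan says.** Section 3.4 opens its list with "The investigator/sub-investigator should discontinue the study if any of the following criteria are met", so each criterion is sufficient on its own. Criterion 3 is symptomatic CPK elevation: CPK above 1.5 × ULN "with severe unusual myalgia, muscular weakness, or muscle twitching". The Synopsis repeats this criterion with the same connector.

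Section 5.4.4.1 tells sites what to do when CPK rises after dosing starts. Its last instruction concerns the same named event at the same threshold, here "accompanied by unusual severe myalgia, muscular weakness, and muscle twitching", and states that "the study will be discontinued (see Section 3.4, Discontinuation Criteria for Individual Subjects".

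Section 3.4 also has a separate criterion 4: "Any event of myopathy defined as severe unusual myalgia, muscular weakness, and muscle twitching". It applies at any CPK level and adds a condition on persistence or rapid worsening.

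All of this is current protocol text. The difference does not come from the superseded version 1.3 excerpt in Appendix 7.

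**The concern.** A discontinuation rule for a recognised laboratory effect of the drug should have one definition. Here the threshold, the symptoms and the consequence agree, but the connector does not, and it decides whether one symptom is enough or all three are needed. Section 5.4.4.1 is the section a site would naturally open when a raised CPK result arrives, and it gives a complete definition before it points elsewhere. A reader has no reason to suspect that the section it points to says something different. One who checks finds two definitions and no rule of precedence.

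What is at stake is whether the criterion is recognised in a subject who has a raised CPK and some, but not all, of the symptoms. A smaller matter is that the SAP summarises premature discontinuations by primary reason (Section 7.2.1) and adverse events leading to permanent discontinuation (Section 7.5.1.1). Uneven application could therefore carry into those counts.

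**Working it through.** No sample-size, power or error-rate figure is involved. The check compares the passages and counts the cases in which they differ.

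**Side by side**

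| Element | Section 3.4 criterion 3 and Synopsis | Section 5.4.4.1, last instruction |
|---|---|---|
| CPK threshold | above 1.5 × ULN | above 1.5 × ULN |
| Symptoms | myalgia, weakness, twitching | myalgia, weakness, twitching |
| Connector | 'or' | 'and' |
| Consequence | discontinuation | discontinuation, referring to Section 3.4 |

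**Counting the symptom patterns.** Take CPK above 1.5 × ULN as given and treat each symptom as present or absent. There are 2 × 2 × 2 = 8 patterns.

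- 'Or' is met by every pattern except none present: 8 − 1 = 7.
- 'And', read literally, is met only when all three are present: 1.
- The wordings differ in 7 − 1 = 6 patterns: 3 with exactly one symptom and 3 with exactly two.

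This counts patterns, not subjects. The patterns are not equally likely, so 6 of 8 is not a proportion of patients.

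**Following one subject through Section 5.4.4.1.** Suppose CPK is 4 × ULN with one of the three symptoms (an illustrative case), and take asymptomatic in its ordinary sense of having no muscle symptoms.

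1. The first instruction (above 3 × ULN) is limited to asymptomatic subjects, so it does not apply.
2. The second (already above 3 × ULN at baseline, then more than doubled) has the same limit, so it does not apply.
3. The third requires CPK above 10 × ULN; 4 is below 10, so it does not apply.
4. The fourth, with a literal 'and', needs all three symptoms, so it does not apply.

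The section then gives no specific instruction. Under Section 3.4 criterion 3 the same subject qualifies, because 4 exceeds 1.5 and one symptom is enough.

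**Does criterion 4 close the gap?** No. Read literally it also needs all three symptoms, together with its time-course condition.

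**How many subjects?** Section 1.3 gives the frequency of blood creatine phosphokinase increased as an adverse event over the overall period, for the 100 mg and 150 mg groups: 9.6% and 10.8% in RAJ3, 5.7% and 11.5% in RAJ4. These figures cannot be turned into the size of the gap. Under Section 5.5.1 an abnormal laboratory value becomes an adverse event only if it meets one of the listed conditions, so the percentages are not the rate of CPK above 1.5 × ULN. Nor do they say how many subjects had muscle symptoms.

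**The case against.** The best case on the other side is that the passages can be obeyed together. All three symptoms is a special case of any one symptom, so a site that follows Section 3.4 also satisfies Section 5.4.4.1. The sentence in Section 5.4.4.1 points to Section 3.4, the dedicated discontinuation section, and the Synopsis agrees with it. The 'and' may be loose list wording: RAJ1 exclusion criterion 13 in Section 3.3 uses 'and' in a list that is plainly illustrative. Discontinuation criteria 7 and 12 in Section 3.4 and suspension criterion 5 in Section 3.4.1.1 let the investigator act in the subject's interest in any event. A targeted muscle examination and a questionnaire accompany CPK monitoring.

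Much of this stands, and it limits the consequence. It does not remove the inconsistency. Criteria 3 and 4 of Section 3.4 use 'or' and 'and' next to each other for the same three symptoms, so a site cannot assume that the connectors are interchangeable. RAJ1 exclusion criterion 12 in Section 3.3 also uses 'or' when it defines symptomatic CPK elevation, so the one term carries two meanings in the protocol. Discretion to stop is not the same as a stated criterion for stopping.

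Three stronger readings are tempting, and the documents do not support them:

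- A reader might infer that Section 5.4.4.1 directs a subject with one or two symptoms to stay on treatment. It does not; it is silent on that subject.
- A reader might take the 5.7% to 11.5% as the share of subjects caught in the gap. Those are reported CPK-increased events. Section 1.4 describes the CPK increases commonly seen to date as showing no evidence of myopathy, and Section 1.3 says that none of the four such events in the psoriasis study had symptoms suggesting it.
- A reader might conclude that discontinuations cannot be compared across the approximately 170 centers. No between-center comparison is planned, the study is open-label without allocation, and SAP Appendix 1 rules out hypothesis testing for efficacy. Some effect on the discontinuation counts is possible, but none is shown.

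**Conclusion.** The inconsistency is real and lies in operative text. The same discontinuation event is defined with 'or' in Section 3.4 criterion 3 and the Synopsis and with 'and' in Section 5.4.4.1, and nothing states which prevails. The wordings part for every subject with CPK above 1.5 × ULN and exactly one or two of the symptoms. For that subject Section 3.4 calls for discontinuation, Section 5.4.4.1 does not trigger it, and the retest instructions there do not apply either.

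The practical risk is that a site relying on Section 5.4.4.1 alone misses the criterion. The number of subjects exposed to that risk cannot be derived from the documents and may be very small. The conclusion rests on reading 'and' literally and asymptomatic in its ordinary sense; a looser reading of 'and' narrows the gap. Confidence is high that the wordings differ and lower about how often it would matter. The point should be corrected because it concerns subject safety and is cheap to settle, not because it threatens the analysis.

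**What to change.** Bring the Synopsis, Section 3.4 criterion 3 and Section 5.4.4.1 to one identical definition, or have Section 5.4.4.1 refer to Section 3.4 without restating the symptoms. Which connector is intended is for the sponsor's clinical team to decide. The same edit should make sure that Section 5.4.4.1 does not leave a subject who is neither asymptomatic nor within the stated definition without any instruction.

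The cost is a wording correction under Section 8.3.3, with whatever ethics-committee approval or notification that requires, and a clarification letter to sites. Sample size, visit schedule and planned analyses are unaffected. If treatment has already ended, the clinical study report should state which reading sites applied, so that CPK-related discontinuations can be interpreted.

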#### 5.4.4.2 Liver Safety Monitoring and Assessment

If laboratory testing for a subject enrolled in a study and receiving the study drug reveals  $> 3 \times \text{ULN}$  elevation in serum aminotransferases (ALT, AST) or TBL elevation to  $> 2 \times \text{ULN}$ , the liver function test must be repeated including at least the 4 parameters ALT, AST, ALP,

- CONFIDENTIAL -

and TBL. The retest is to be performed between 48 hours and 72 hours after notification of the test results.

See Appendix 6 “Liver Safety Monitoring and Assessment” for the assessment of additional information and liver function values in the monitoring.

If a subject enrolled in a study and receiving the study drug reveals  $> 3 \times$  ULN elevation in serum aminotransferases (ALT, AST) concurrently with bilirubin  $> 2 \times$  ULN, the investigator will decide whether the event is SAE. Even if the abnormal change is not considered by the investigator or sub-investigator to be SAE, it has to be reported to the sponsor or CRO as in the case of SAE.

#### **5.4.5 Physical Examination**

A physical examination will be performed at each study visit and during unscheduled visits, if necessary, to confirm physical findings, in accordance with Table 1, Schedule of Assessments.

A symptom directed physical exam for RA will be performed at all study visits.

#### **5.4.6 12-lead Electrocardiogram (ECG)**

A 12-lead ECG will be obtained at the study visits every 48 weeks from Week 0 onward according to Table 1, Schedule of Assessments, as well as at end of treatment/early termination. The investigator or sub-investigator will confirm the ECG chart, assess the results as “normal,” “abnormal but not to a clinically significant degree,” and “clinically significant abnormality” and record the results of the assessment in the CRF. If the finding is “abnormal but not to a clinically significant degree” or “clinically significant abnormality,” the finding will be recorded in the CRF.

In addition, the clinical interpretation of the 12-lead ECG performed at Week 0 must be completed before the first dose of the study drug.

#### **5.4.7 Radiography**

Chest radiography will be obtained at the study visits every 48 weeks from Week 0 onward according to Table 1, Schedule of Assessments, as well as at end of treatment/early termination. However, chest radiography at end of treatment/early termination need not be performed if data obtained within 24 weeks prior to the end of treatment/early termination are available. The investigator or sub-investigator will read the chest radiographs, assess the result as “normal,” “abnormal but not to a clinically significant degree,” or “clinically significant abnormality” and record the results of the assessment in the CRF. If the finding is “abnormal but not to a clinically significant degree” or “clinically significant abnormality,” the finding will be recorded in the CRF.

- CONFIDENTIAL -

## 5.5 Adverse Events and Other Safety Aspects

### 5.5.1 Definition of Adverse Events (AEs)

An AE is defined as any untoward medical occurrence in a subject administered a study drug that does not necessarily have a causal relationship to this treatment. An AE can therefore be any unfavorable and unintended sign (including an abnormal laboratory finding), symptom, or disease temporally associated with the use of a study drug, whether or not related to the study drug.

All AEs newly observed in the period from the first dose of study drug to end of study (at time of follow-up) or spontaneously reported AEs will be recorded in the medical record or other source document, as well as in the CRF. If a concurrent disease has clearly worsened to an extent that exceeds the usual course after the first dose of the study drug, it will be mentioned among the AEs as a worsening of a concurrent disease. If an AE recurs after having temporarily disappeared, it will be handled as a new AE.

An abnormality identified during a medical test (e.g., laboratory parameter, vital sign, ECG data, physical examination) should be defined as an AE only if the abnormality meets one of the following criteria:

- Induces clinical signs or symptoms
- Requires active intervention
- Requires suspension, interruption, or discontinuation of study medication
- The abnormality or laboratory test value is clinically significant based on the opinion of the investigator or other responsible personnel

The particulars to be noted with respect to the AE are the name of the event, date of onset, date of disappearance, severity (at peak time), seriousness, treatment of the study drug, other treatment, outcome, causal relationship to the study drug, and rationale for the assessment of causal relationship. Recording the rationale for the assessment of causal relationship for all AEs is not required; this should be handled at the sponsor's request. The severity of each event should be recorded on a scale of Grade 1 to Grade 5 in the CRF, and the causal relationship to the study drug should be recorded as "Probably," "Possible," or "Not related" (see Section 5.5.3, Criteria for Causal Relationship to the Study Drug, and Section 5.5.4, Criteria for Defining the Severity of an Adverse Event). The treatment of the AE (whether it was treated with pharmacotherapy or by other means) and the treatment of the study drug should be recorded in the medical record or other source document, as well as in the CRF. The outcome should be recorded in the medical record or other source document, as well as the CRF, as "resolved," "alleviated," "unresolved," "resolved but with late effect," "death," or "unknown."

### 5.5.2 Definition of Serious Adverse Events (SAEs)

An AE is considered "serious" if, in the view of either the investigator or sponsor, it results in any of the following outcomes:

- Results in death.

- CONFIDENTIAL -

- Is life threatening (an AE is considered “life-threatening” if, in the view of either the investigator or sponsor, its occurrence places the subject at immediate risk of death. It does not include an AE that, had it occurred in a more severe form, might have caused death).
- Results in persistent or significant disability/incapacity.
- Results in congenital anomaly or birth defect.
- Requires inpatient hospitalization or leads to prolongation of hospitalization (Hospitalization for treatment/observation/examination caused by AE is considered to be serious).
- Other medically important events

Medical and scientific judgment should be exercised in deciding whether expedited reporting is appropriate in other situations, such as important medical events that may not be immediately life-threatening or result in death or hospitalization but may jeopardize the subject or may require intervention to prevent any of the other outcomes listed in the definition above. These events, including those that may result in disability/incapacity, should also usually be considered serious. Examples of such events are allergic bronchospasm requiring intensive treatment in an emergency room or at home; blood dyscrasias or convulsions that do not result in hospitalization; or development of drug dependency or drug abuse.

In addition, all sponsor’s clinical studies have the requirement that all of the medical events described in Appendix 3 “Events Always Considered to be Serious” and Appendix 6 “Liver Safety Monitoring and Assessment” be reported by the investigator as SAEs even if they do not meet the aforementioned conditions.

### 5.5.3 Criteria for Causal Relationship to the Study Drug

AEs that fall under either “Possible” or “Probable” should be defined as “AEs whose relationship to the study drugs could not be ruled out.”

Causal Relationship to Study Drug	Related Assessment Criteria
Not related	A clinical event, including laboratory test abnormality, with a temporal relationship to drug administration which makes a causal relationship improbable, and/or in which other drugs, chemicals or underlying disease provide plausible explanations.
Possible	A clinical event with a reasonable time sequence to administration of the drug, to which one of the following applies: 
 
• Could also be explained by concurrent/underlying disease or other drugs
 
• Information on drug withdrawal is lacking or unclear
 

Probable	A clinical event with a reasonable time sequence to administration of the drug, to which one of the following applies: 
 
• Recurs upon re-administration of the drug, or disappears or is alleviated when the drug is withdrawn
 
• Cannot be explained by concurrent/underlying disease or other drugs, or is unlikely to be attributable to them
 

- CONFIDENTIAL -

#### 5.5.4 Criteria for Defining the Severity of an Adverse Event

The AE grades will be based on NCI-CTCAE [Japan Clinical Oncology Group (JCOG), 2011]. Items unspecified by these criteria will be assessed according to the following criteria and recorded.

Grade	Assessment Criteria
Grade 1 (Mild)	Mild; asymptomatic or mild symptoms, clinical or diagnostic observations only; intervention not indicated.
Grade 2 (Moderate)	Moderate; minimal; local or noninvasive intervention indicated; limiting age-appropriate instrumental ADL.
Grade 3 (Severe)	Severe or medically significant but not immediately life-threatening; hospitalization or prolongation of hospitalization indicated; disabling; limiting self-care ADL.
Grade 4 (Life threatening or incapacitating)	Life-threatening consequences; urgent intervention indicated.
Grade 5 (Death)	Death related to AE.

#### 5.5.5 Reporting of Serious Adverse Events (SAEs)

In the case of an SAE, the investigator/sub-investigator must report the SAE to the head of the study center and also contact the sponsor by telephone, e-mail, or fax immediately (within 24 hours of awareness) [in case of Japan: in addition to reporting to the head of the study center].

The investigator should complete and submit an SAE report containing all information that is required by the regulatory authorities to the sponsor or CRO [in case of Japan: and to the head of the study center] by e-mail or fax immediately (within 24 hours of awareness). If e-mail transmission or faxing of an SAE report is not possible, or is not possible within 24 hours, the sponsor or delegated CRO should be informed by phone.

For contact details, see SECTION II, CONTACT DETAILS OF KEY SPONSOR'S PERSONNEL.

Send the SAE report to the below FAX number.

Contact Information for the Sponsor

[REDACTED]

TEL: [REDACTED], FAX: [REDACTED]

Contact Information for the CRO

Japan:

[REDACTED]

TEL: [REDACTED] FAX: [REDACTED]

Korea:

- CONFIDENTIAL -

████████████████████  
TEL: ██████████, FAX: ██████████

Taiwan:

████████████████████  
TEL: ██████████, FAX: ██████████

